## 1.5 STUDY RATIONALE

Belumosudil is an inhibitor of the ROCK2 isoform. This family of kinases has been shown to have profound activity on cell morphology, motility, and shape through effects on the cytoskeleton. Data show that ROCK2 inhibition has an anti-inflammatory effect predominantly through the down-regulation of signal transducer and activator of transcription 3 (STAT3) and the Th17 axis. Thus IL-17, IL-21, and IL-22 are downregulated.

Chronic fibrosis is characterized by myofibroblast resistance to apoptosis. Inhibition of the ROCK pathway has demonstrated a beneficial effect on bleomycin induced fibrosis acting through the inhibition of activation of myofibroblasts. Anti-inflammatory activity, coupled with anti-fibrotic activity, suggests that inhibiting the ROCK2 pathway may be an effective therapy for inflammatory fibrotic diseases such as lung disease, which is associated with the majority of subjects with systemic sclerosis (SSc). Belumosudil has been shown to increase STAT5, which leads to an increase in the Treg population of lymphocytes and helps balance the immune system during inflammation.

Nonclinical pharmacology studies have demonstrated the potential of belumosudil to have a therapeutic benefit in a number of indications, particularly in autoimmune and fibrotic diseases. In vitro, belumosudil has demonstrated an impact on the Th17-type immune responses as well as on the actin/myosin cytoskeletal network and collagen formation. In vivo, belumosudil has demonstrated efficacy in a variety of clinically

relevant animal models of disease including cGVHD, scleroderma, IPF, and other autoimmune diseases at clinically relevant drug exposures. Belumosudil has also been shown to significantly decrease the GVHD score in the sclerodermatous GVHD mouse model.

In a 3-month study in patients with moderate-to-severe psoriasis, belumosudil demonstrated both clinical and pharmacodynamic (PD) activity. Similarly, in an open-label study of belumosudil in the treatment of IPF, belumosudil slowed the decrease in lung function in IPF patients over 24 weeks of treatment when compared to best supportive care. Finally, in a study of patients with steroid refractory or dependent cGVHD, approximately two-thirds of patients achieved a clinical response with belumosudil. In this study, patients were able to reduce doses of steroids and immunosuppressant drugs during treatment with belumosudil. It is noteworthy that cGVHD represents a paradigm for immune-inflammatory triggering of chronic fibrosis that shares important similarities with SSc.

## 1.6 DOSE RATIONALE

Belumosudil was well-tolerated in Phase 1 studies of healthy volunteers at single doses up to 1000 mg, and with repeat doses up to 500 mg BID for 28 days.

Phase 2 studies of belumosudil have been initiated, enrolling patients with IPF (KD025-207), cGVHD (Study KD025-208 and Study KD025-213) and psoriasis (Study KD025-205, Study KD025-206, and Study KD025-211). More than 600 subjects have been dosed with belumosudil for inflammatory or fibrotic diseases or as healthy volunteers at doses ranging from 20 mg to 1000 mg QD and 500 mg BID.

Preliminary data from phase 2 studies of belumosudil indicate that the dose of 200 mg QD is associated with clinical efficacy and should be well-tolerated in an indication with immune and fibrotic manifestations (e.g., diffuse cutaneous systemic sclerosis [dcSSc]).

This study will evaluate belumosudil at a dose of 200 mg BID in an open study in dcSSc to further evaluate safety and activity.

Also, refer to the [Belumosudil IB](#) for more detailed information.

## 2. STUDY OBJECTIVES

## 2.1 PRIMARY OBJECTIVE

The primary objective of this study is to evaluate the efficacy of belumosudil using the Combined Response Index in diffuse cutaneous Systemic Sclerosis (CRISS) at Week 24.

## 2.2 SECONDARY OBJECTIVES

- To assess CRISS at Weeks 8, 16, 36, and 52
- To evaluate the efficacy of belumosudil at Week 24 for:
  - Modified Rodnan Skin Score (mRSS)
  - FVC
  - Physician Global Assessment
  - Patient Global Assessment
  - Scleroderma Health Assessment Questionnaire–Disability Index (SHAQ-DI)
- To evaluate the efficacy of belumosudil at Weeks 8, 16, 36, and 52 compared to baseline for all subjects for the parameters in the bullet above
- To assess the safety of belumosudil in subjects with dcSSc by examining the percentage of subjects with treatment-emergent adverse events (Common Terminology Criteria for Adverse Events Version 5.0 [CTCAE v5.0])

## 2.3 EXPLORATORY OBJECTIVES

### 3. INVESTIGATIONAL PLAN

#### 3.1 STUDY DESIGN

This is a phase 2, open-label, single cohort, multicenter trial in subjects with dcSSc.

The duration of the study will be approximately 14 months (4 weeks for screening, 52 weeks of dosing period, and 4 weeks of follow-up).

Subjects who have signed an Institutional Review Board/Independent Ethics Committee-(IRB/IEC)-approved informed consent form and met all of the inclusion/exclusion criteria will be enrolled. A total of 12 to 15 subjects will receive belumosudil 200 mg administered PO BID for 52 weeks.

Subjects will undergo evaluations as outline in the Study Schedule of Assessments ([Appendix A](#)). The primary endpoint will be analyzed using Week 24 data.

Efficacy will be assessed throughout the 52-week dosing period using CRISS, mRSS, PFTs, Physician Global Assessment, and Patient Global Assessment.

#### Follow-up Period

A 4-Week Safety Follow-up Visit will occur 28 days ( $\pm$  3 days) after the last dose of study drug. Subjects will undergo PEs; vital sign measurements; weight measurement; blood sample collection for hematology and chemistry; urinalysis; ECGs; AE assessments; concomitant medication assessments; and pregnancy testing for females of childbearing potential. In addition, subjects will also have efficacy assessment done as per [Appendix A: Schedule of Assessments](#).

#### 3.2 NUMBER OF SUBJECTS

Twelve to 15 male and female subjects will be enrolled.

#### 3.3 STUDY CENTERS

Approximately 5 to 6 centers will participate in this study.

#### 3.4 INCLUSION CRITERIA

1. Male and female subjects  $\geq$  18 years old with the diagnosis of dcSSc according to the 2013 American College of Rheumatology and European League Against Rheumatism criteria

2. Must have disease duration (defined as interval from first non-Raynaud disease manifestation) of  $\leq$  6 years
3. Must have mRSS  $\geq$  15 but  $\leq$  40
4. Must have active disease as determined by the Principal Investigator within the 6 months prior to screening
5. Adequate organ and bone marrow functions evaluated during the 28 days prior to enrollment as follows:
  - a. Absolute neutrophil count  $\geq 1.5 \times 10^9/L$
  - b. Platelet count  $\geq 100 \times 10^9/L$
  - c. Total bilirubin  $\leq 1.0 \times$  upper limit of normal (ULN)
  - d. Alanine aminotransferase (ALT), aspartate aminotransferase (AST), and serum creatinine  $\leq 1.5 \times$  ULN
6. Female subjects of childbearing potential have a negative pregnancy test at screening. Females of childbearing potential are defined as sexually mature women without prior hysterectomy or who have had any evidence of menses in the past 12 months. However, women who have been amenorrheic for 12 or more months are still considered to be of childbearing potential if the amenorrhea is possibly due to prior chemotherapy, anti-estrogens, or ovarian suppression.
  - a. Women of childbearing potential (i.e., menstruating women) must have a negative urine pregnancy test (positive urine tests are to be confirmed by serum test) documented within the 24-hour period prior to the first dose of study drug.
  - b. Sexually active women of childbearing potential enrolled in the study must agree to use two forms of accepted methods of contraception during the course of the study and for 3 months after their last dose of study drug. Effective birth control includes (i) intrauterine device plus 1 barrier method; (ii) on stable doses of hormonal contraception for at least 3 months (e.g., PO, injectable, implant, transdermal) plus 1 barrier method; or (iii) 2 barrier methods. Effective barrier methods are male or female condoms, diaphragms, and spermicides (creams or gels that contain a chemical to kill sperm), or a vasectomized partner.
7. For male patients who are sexually active and who are partners of premenopausal women: agreement to use 2 forms of contraception as in criterion number 6b above during the treatment period and for at least 3 months after the last dose of study drug.
8. Male subjects must not donate sperm for 3 months after last dose of study drug.

---

9. Able to provide written informed consent prior to the performance of any study-specific procedures.

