### 5.2.1 Week 1 Day 1 Visit (Baseline)

At the Week 1 Day 1 Visit, subjects will come to the clinic to have the following procedures:

- Confirmation of inclusion/exclusion criteria
- mRSS
- SHAQ-DI
- Physician Global Assessment
- Patient Global Assessment
- PFT\*
- Skin biopsies
- Complete PE
- Vital signs
- Weight
- Hematology and chemistry\*
- Urinalysis\*
- 12-lead ECG
- Pregnancy test
- Dispense study diary
- Study drug administration (belumosudil 200 mg): review with subject
- Dispense study drug
- Concomitant medication assessment
- AE assessment

*\*These assessments do not need to be repeated if they were conducted within 7 days of baseline.*

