### 6.2.5 Pregnancy Testing

[figure not shown]
Pregnancy tests (urine) will be done in women of childbearing potential. Positive urine results are to be confirmed with serum testing. In the event of a positive urine test at baseline, serum testing results should be acquired within 48 hours prior to study start.

In the event that a subject, or subject's partner, becomes pregnant while on study, she will be monitored until the outcome of the pregnancy is known. The baby will continue to be monitored for 30 days after delivery. The data are reported on a pregnancy form within 24 hours of becoming aware.

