- H. Women of childbearing potential must have a negative urine pregnancy test. Positive results are to be confirmed with serum testing. In the event of a positive urine test at baseline, serum testing results should be acquired within 48 hours prior to study start.

Note: At Week 1 Day 1 visit, if screening was completed within 7 days of baseline, only the complete PE and vital sign measurements need to be repeated.

Note: CRISS will not be performed on site but rather will be calculated outside of EDC.

[figure not shown]

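### Criterion 6a's gloss on menstruating women contradicts criterion 6, and the Appendix A 7-day note contradicts the scheduled Day 1 pregnancy test (minor, patient safety only)

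*Protocol*

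**What the plan says.** **Who counts.** Protocol 3.4, criterion 6, requires a negative pregnancy test at screening. It defines females of childbearing potential as "sexually mature women without prior hysterectomy or who have had any evidence of menses in the past 12 months". It then adds that women amenorrheic for 12 months or more are "still considered to be of childbearing potential if the amenorrhea is possibly due to prior chemotherapy, anti-estrogens, or ovarian suppression".

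**The 24-hour rule.** Criterion 6a, in the same words in the Synopsis, says "Women of childbearing potential (i.e., menstruating women) must have a negative urine pregnancy test", documented in the 24 hours before first dose.

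**The Day 1 visit.** Section 5.2.1 lists a pregnancy test. Its footnote, "These assessments do not need to be repeated if they were conducted within 7 days of baseline", attaches only to asterisked items: PFT, hematology and chemistry, and urinalysis. The pregnancy test has no asterisk. The Appendix A grid marks the test at both screening and Week 1.

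**The note.** Under the same grid, a note on the Week 1 Day 1 visit says that "if screening was completed within 7 days of baseline, only the complete PE and vital sign measurements need to be repeated".

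**Other testing text.** Section 6.2.5 says "Pregnancy tests (urine) will be done in women of childbearing potential", and Appendix A footnote H says "Women of childbearing potential must have a negative urine pregnancy test". Neither carries the gloss, and neither sets a 24-hour window. Section 6.2.5 also says "In the event of a positive urine test at baseline, serum testing results should be acquired within 48 hours prior to study start", which takes for granted that a urine test is done at baseline.

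**The concern.** There are two separate wording conflicts in rules that sites apply.

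First, the abbreviation in 6a equates the defined group with women who menstruate. A woman whose periods have stopped because of ovarian suppression belongs to the group under criterion 6 but not under the gloss. Since 6a is the only text with a 24-hour window, a literal reader would not apply that window to her.

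Second, the pregnancy test is on the screening list in 5.1, so on Day 1 it is a repeat. The Appendix A note restricts repeats to two items, and the pregnancy test is not one of them.

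What is at stake is a first dose given on an outdated pregnancy test. Protocol 1.3 reports embryo-fetal toxicity and teratogenicity in nonclinical studies of belumosudil. The question is one of subject protection, not of analysis.

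**Working it through.** The plan states no figure to reproduce. The check sets every pregnancy-test provision side by side.

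| Place | Who is covered | When | Gloss? |
|---|---|---|---|
| 3.4 criterion 6 | childbearing potential as defined, including the named amenorrheic group | screening | no |
| 3.4 and Synopsis, 6a | childbearing potential, equated with menstruating | within 24 hours before first dose | yes |
| 5.2.1 | listed for the visit, no asterisk | Day 1 | no |
| Appendix A grid | row marked at screening and Week 1 | Day 1 | no |
| Appendix A footnote H, 6.2.5 | childbearing potential | no 24-hour window; 48 hours for serum confirmation of a positive urine test only | no |
| Appendix A note | not stated | Day 1 repeat not required if screening ended within 7 days | n/a |

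**Step 1, the gloss.** The group named in the second part of criterion 6 has been without periods for at least 12 months. Those women cannot be menstruating women, so 6a and criterion 6 disagree about them on any reading.

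**Step 2, the note.** The items both listed at screening (5.1) and listed on Day 1 without an asterisk (5.2.1) include mRSS, weight, 12-lead ECG and the pregnancy test, besides the complete PE and vital signs. The note keeps only the last two. It therefore conflicts with 5.2.1 for four items, of which the pregnancy test is the one with a safety deadline.

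**Step 3, age of the last negative test at first dose.**

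| Woman | Text followed | Age of test |
|---|---|---|
| Menstruating | 6a | at most 24 hours |
| Menstruating | note | about 7 days, in breach of 6a |
| Named amenorrheic group | 5.2.1 and grid | tested on Day 1 |
| Named amenorrheic group | gloss read literally, plus note | about 7 days |
| Either, screening completed more than 7 days before baseline | note does not apply | tested on Day 1 |

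In hours, 7 days is 7 × 24 = 168, against a limit of 24.

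**Step 4, what separates the two conflicts.** The second needs no help from the first: a menstruating woman screened more than 24 hours before dosing is caught between the note and 6a. For the named amenorrheic group, the gloss alone does not remove the Day 1 test. It takes the gloss and the note together.

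**The case against.** The strongest reply is that the rest of the protocol settles the matter. Criterion 6 is an explicit definition and 6a is its sub-item, so the gloss can be taken as loose shorthand that the definition overrides. Section 5.2.1, the grid, footnote H and 6.2.5 all point to a Day 1 test. Section 5.2.1 also has eligibility confirmed on Day 1, so 6a still binds for the women it reaches. This stands as a limit on severity, since a site working from 5.2.1 will do the test. It does not remove the contradictions. No text says which provision prevails, and the note addresses exactly this situation beneath the schedule itself.

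A reader might infer four stronger points, which the documents do not support.

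- **Every woman with a uterus falls in the gap, because the definition uses *or*.** On that reading the sentence retaining certain amenorrheic women would add almost nothing. It makes sense only if 12 months without periods otherwise takes a woman out. The firm contradiction is confined to the group that sentence names. Any looseness in the *or* is a separate drafting matter.
- **Most women in the trial could be affected.** Applying the disease's female share from Protocol 1.1 to 12 to 15 subjects counts all the women enrolled, not those affected. The documents give no basis for the latter.
- **The test could be as old as the 29-day screening window.** That needs screening spread over many days, whereas 5.1 and Appendix A describe a single screening visit.
- **An endpoint is disturbed because the note also drops the Day 1 mRSS.** SAP 3.1.5 takes the last valid value within 29 days before first dose, so the screening score would serve as baseline.

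**Conclusion.** Both provisions are wrong as written. The matter is minor and concerns patient safety only. The gloss in 6a excludes, if read literally, the amenorrheic women whom criterion 6 expressly keeps in. The Appendix A note would waive a Day 1 pregnancy test that 5.2.1 and the grid require and, for menstruating women, that 6a may require as well.

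The size is a last negative test about 7 days old at first dose in place of at most 24 hours. This assumes a single screening visit completed within 7 days of baseline and a site that follows the note. The number of women affected is not given and is likely small. No woman of childbearing potential is left wholly untested: the screening test in criterion 6, contraception in 6b and the pregnancy exclusion in 3.5 still apply. Confidence is high that the texts conflict. Whether any site would act on the faulty wording cannot be told from the documents.

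**What to change.** 1. In criterion 6a, in both section 3.4 and the Synopsis, replace the parenthesis about menstruating women with *(as defined in criterion 6)*.
2. Amend the Appendix A note so that the Day 1 pregnancy test is always done in women of childbearing potential. Preferably, align the whole note with 5.2.1: only PFT, hematology and chemistry, and urinalysis may be skipped if done within 7 days of baseline, and every other Day 1 item is performed. This also resolves the conflicts over mRSS, weight and ECG.

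The cost is a few words in three places. The added testing burden is about nil, because 5.2.1 and the grid already schedule the Day 1 pregnancy test. Endpoints, populations and analyses stay as they are.

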### **3.5 EXCLUSION CRITERIA**

1. Subject has corrected QT interval using Fridericia's formula (QTcF) > 450 ms
2. Ongoing use or current use of concomitant medication known to have the potential for QTc prolongation
3. Female subject who is pregnant or breastfeeding.
4. Participated in another study with an investigational drug within 28 days of study entry (for studies involving biologics, within three half-lives of the biologic).
5. History or other evidence of severe illness or any other conditions that would make the subject, in the opinion of the Investigator, unsuitable for the study.
6. Chronic heart failure with New York Heart Association Classes II, III, and IV.
7. Active or chronic liver disease (e.g., cirrhosis).
8. Positive human immunodeficiency virus (HIV) test.
9. Active hepatitis C virus (HCV), hepatitis B virus (HBV), or positive whole blood tuberculin test.
10. Diagnosed with any malignancy within 3 years of enrollment, with the exception of basal cell or completely resected squamous cell carcinoma of the skin, resected in situ cervical malignancy, resected breast ductal carcinoma in situ, or low-risk prostate cancer after curative resection.
11. Has had previous exposure to belumosudil or known allergy/sensitivity to belumosudil or any other ROCK2 inhibitor.
12. Scleroderma renal crisis within 4 months prior to enrollment.
13. FVC  $\leq$  50% Predicted.

### **3.6 SCREENING**

The screening period commences once the ICF is signed. Adequate time must be allowed for the subject to ask questions and make a voluntary decision. The ICF must be signed before any study-specific samples are taken or study-specific tests or evaluations are conducted.

Data regarding screen-failures will be captured in the electronic data capture (EDC) system.

Screening assessments as summarized in the Schedule of Assessments ([Appendix A](#)) will be performed within 29 days of first dose of study drug (Week 1 Day 1 Visit [baseline]).

Study eligibility will be based on satisfying all of the study inclusion and exclusion criteria.

Re-screening of subjects will be allowed only upon approval of the medical monitor.

### **3.7 WITHDRAWAL CRITERIA**

Subjects may be withdrawn from study treatment at any time by the Investigator if it is considered detrimental for the subject to continue in the study. The reason for withdrawal must be captured in the electronic case report form (eCRF).

Subjects have the right to withdraw from the study at any time and for any reason without prejudice to their future medical care by the physician or at the institution. Every effort should be made to have such subjects attend end of treatment (EOT) and 28-day Follow-up Visits. In the instances where a reason for withdrawal of consent is given, this will be captured in the eCRF. Subject data up to withdrawal of consent will be included in the analysis of the study, and where permitted, publicly available data can be included after withdrawal of consent.

### **3.8 REPLACEMENTS**

Subjects withdrawn from the study before receiving any study drug will be replaced by enrolling additional subjects into the study.

### **3.9 TREATMENT DISCONTINUATION**

Treatment discontinuation reasons include the following:

- An AE requiring permanent discontinuation of study drug
- Investigator decision
- Clinically significant disease progression. For example:
  - mRSS increase  $\geq$  5 units
  - Absolute decrease in FVC (% predicted)  $\geq$  10% or absolute decrease in diffusing capacity of the lungs for carbon monoxide (DLco) (corrected for Hb) of  $\geq$  15%
  - Renal crisis
- Study stopping rules for the sponsor ([Section 9.6.1](#))
- Subjects meeting criteria for discontinuation from the study ([Section 9.6.2](#))
- Voluntary withdrawal by subject
- Noncompliance to protocol
- Subject lost to follow-up
- Termination of the study by sponsor

- Subject death

## 4. STUDY TREATMENT

### 4.1 INVESTIGATIONAL PRODUCT

Belumosudil (2-(3-(4-(1H-indazol-5-ylamino) quinazolin-2-yl) phenoxy)-N-isopropylacetamide-methane sulfonic acid salt) is an orally available ROCK2 selective inhibitor. Belumosudil will be provided as 200 mg tablets.

### 4.2 DOSAGE AND ADMINISTRATION

Subjects will receive belumosudil 200 mg PO BID for 52 weeks.

### 4.3 TREATMENT ASSIGNMENT

This is a single-cohort study. All subjects will receive belumosudil 200 mg PO BID for 52 weeks.

### 4.4 BLINDING

This is an open-label study. No blinding will occur.

### 4.5 TREATMENT COMPLIANCE

Subjects will be given a study drug diary to record the details of each dose of study drug. Diaries will be dispensed/collected on each visit. Compliance with PO dosing will be confirmed using subject diaries, which will be examined at each visit by site staff to determine if dosing is as instructed per protocol and follow-up with the subject accordingly. If the subject skips more than 7 consecutive days of drug dosing (other than those specified in the Dose Modification Guideline for Toxicity), the subject should be discontinued from the study unless approved by the medical monitor and Investigator.

